4.0 Enrollment / Randomization

1. Subjects with a clinical diagnosis of lymphedema following axillary lymph node removal including breast cancer related surgery will be made aware of the study by recruitment flyers and / or their health care clinician, who will ask the patient if they would like for a member of the research team to contact them regarding potential participation in the research study. If the patient would like to receive more information about participating in the study and like to be contacted by a KSP in the study, then the clinician will provide the patient's preferred contact information to a KSP member. The patient will then be contacted by the KSP member and the risks and benefits of the study will be described. Importantly, the treating clinician will only ask if the patient would like to receive more information about the study, but will not be involved in obtaining consent or coercing the patient to participate and the patient will understand there is no change in their clinician care regardless of participation or not in the study. Furthermore, to recruit patients receiving these cancer therapies in local

nonVUMC clinics, we will contact the local clinics using the IRB approved letter and distribute IRB approved flyers to the clinics. Additional patients will be identified using the lymphedema research database where eligible persons request to be on the database to be informed when potential studies become available for the KSP to contact them regarding participation.

2. For Aim 1 and 2 of the study tracking patients near the time of their breast cancer related surgery, we will recruit patients from the One Hundred Oaks Breast Center outpatient clinics seen by the VUMC surgical oncologists and oncologists where the patients are seen for their cancer care. Furthermore, to recruit patients receiving these cancer surgeries in local non-VUMC cancer centers, we will contact the local clinics using the IRB approved letter and distribute IRB approved flyers to the clinics.
3. We will also utilize research databases additional recruitment tools for this protocol. ResearchMatch.org will be utilized as a recruitment tool for this protocol. ResearchMatch.org is a national electronic, web-based recruitment tool that was created through the Clinical & Translational Science Awards Consortium in 2009 and is maintained at Vanderbilt University as an IRB-approved data repository (**see IRB #090207**). SUBJECT LOCATOR will be used as a recruitment tool to identify potential research subjects based on data available in VU clinical systems (e.g. STAR Panel, WizOrder, Clinic Scheduling). The SUBJECT LOCATOR program is part of a toolset available through VICTR that enables teams to specify inclusion/exclusion criteria for a specific study. The inclusion/exclusion criteria are codified for computable use and combined with data coming through VU Clinical Systems to proactively identify individuals who might qualify for a study. Once a 'match' is made, research study personnel are alerted using confidential messaging or a secure web portal and they may then use the information to further review the patient's information using the Vanderbilt Electronic Medical Record. If the patient is further deemed a candidate for the study, the study personnel will notify the patient's care provider who will then ask the patient if they would be interested in communicating with study personnel about research population.
4. IRB approved flyers/advertisements of the study may also be distributed to outpatient clinics and lymphedema support groups/networks as additional means of subject recruitment for the aims of the study.
5. Recruitment of patients will be done through flyers, posted adverts, research match, email, departmental research boards, and those who contact KSP directly using our VUMC website link for interested patient volunteers (<https://ww2.mc.vanderbilt.edu/[name]/50860>).
6. Reporting Workbench Reports (RWB) are available/viewable in eStar. These reports are developed using real-time data and can be customized to meet study-specific inclusion/exclusion criteria. Research team members with eStar access and access to the Report Groups can view/run the reports

as frequently as needed. While the report is generally limited to certain variables, it provides easy access to a patient's record for additional screening and confirmation of eligibility.

A custom RWB report will be utilized to identify potential participants. The report will filter on study inclusion/exclusion criteria computable in the EHR and EMR. Additionally, the report will include OK to Contact status, MHAV account status, and ability to receive MHAV messages. The report may also display additional information that will facilitate screening. We will utilize these systems for MHAV mass messaging and Individual Direct to Patient Messaging for out-reach communication.

5.0 **Study procedures**

1. Informed consent will be obtained via e-consent initially and then during initial visit reviewed in a private setting (e.g., an otherwise empty conference room or waiting area) by one of the study Investigators. This initial e-consent will occur as far in advance of the exam as possible, preferably before the day of the study and a KSP will review any questions with patient remotely as needed prior to onset of study. The study participant will be given a copy of the signed consent form at first visit. The subject will be screened for the study inclusion and exclusion criteria including MRI contraindications or MLD contraindications or precautions to determine eligibility of the study.
2. All subjects will complete an MRI screening form in advance of their scheduled visits for any MRI. The MRI screening form will be cleared by the KSPs and MRI technicians prior to scheduling their 1st MRI visit. This MRI screening form will be completed for each MRI scan a subject may have during the course of the study.
3. The informed consent and the MRI screening form will be sent electronically via email to the participant, to be completed before their study visit.
4. Persons will undergo external measurements obtaining weight, height, arm volumetric measurements (Perometer), skin thickness (SkinFibroMeter), and extracellular fluid levels in the arms (InBODY 770, L-Dex and MoistureMeterD/LymphScanner) and upper body (InBODY 770, MoistureMeterD/LymphScanner) and then undergo a non-invasive MRI to evaluate lymph fluid properties in the upper extremities. No MR methods used require the administration of any exogenous contrast agents, and therefore will be completely non-invasive. The visit for non-MRI and MRI measures lasts

approximately 90minutes. Patients undergoing 2-year monitoring will also undergo these non-MRI measurements at baseline, and every 5-7 months (targeting at 6months) up to 5 total visits within 2 years; and for this same group an MRI will be done at Visit 1 and then as needed based on symptoms, clinical therapies provided increasing risk of lymphedema such as radiation, and non-MRI measures at subsequent follow-up visits within the 2 year time period. For these follow-up visits non-involving MRI, the visits last approximately 30 minutes.

Perometer

L-Dex

LymphaTouch

MoistureMeter D/LymphaScanner

InBODY 770 (Body Composition)

SkinFibroMeter

5. For subjects enrolled in Aim 3 of this study, they will receive the above mentioned non-MRI and MRI measures (#2) at Visits 1, 11, 12 and 22. In addition the MLD screening form will be completed on Visit 1 in preparation for this component of their CDT during subsequent treatment visits, as well as completion of the Functional Outcome Measures (PSFS and UEFI) patient self-reports will be done on Visits 1, 11, 12 and 22 to establish baseline functional level and monitor during treatments. Then they will receive their assigned therapy intervention (CDT alone or CDT with graded negative pressure) at Visits 2-10 and 13-21. For Group 1, the first course of treatment will be CDT alone, then the second course of treatment will be CDT with graded negative pressure. For Group 2, the first course of treatment will be CDT alone, then the second course of treatment will be CDT with graded negative pressure. During all courses of treatment, it will consist of 9 visits within 6-8 weeks at 75minutes duration each visit, twice per week for three weeks and then once per week for 3-5 weeks. There will be a 4-8 week washout period between Visit 11 and Visit 12.
6. For the subgroup of subjects enrolled in the 1 time hourly treatment visit of Aim 3, they will receive the above mentioned MRI and nonMRI measures before and immediately following the 1x hourly treatment. The PSFS and UEFI questionnaires will not be administered for this 1x treatment visit only. The participants will undergo (i.) CDT alone, (ii.) CDT with graded negative pressure, or (iii.) exercise and self management treatment. This subgroup participation may involve undergoing all three of the single treatment options on different study dates if the participant is interested otherwise the study only only involves this one-time study visit.
7. Post processing of this MRI data will be overseen by [name] and performed by [name] or a member of the KSP team. The KSPs analyzing the data in Aim 3 will be blinded of the subjects' group assignments until after data processing and statistically analysis.
8. Images from cases showing examples of findings that correlate with changes in lymphatic structure and function will be de-identified before inclusion in any potential publication or presentation of the results of this pilot study and saved by [name].

9. Compensation will be as follows:
 - a. Aim 1 = \$60
 - b. Aim 2 = \$20 (non-MR measures) / \$40 (MRI)
 - c. Aim 3
 - i. Scan 1 for 1st Treatment = Choice of check for \$60 OR 1 Velcro day and night-time compression wrap for arm and hand
 - ii. If all 9 treatments + exit visit MRI/non-MRI measures complete = \$60
 - iii. After 4-8 month washout period
 - iv. Scan 1 for 2nd Treatment = \$60
 - v. If all 9 treatments + secondary MRI complete = \$60
 - vi. If completes all parts of the study, will earn additional \$50
 - vii. Total = \$120+\$120+\$50 = \$290 OR Total = 1 Velcro compression garment (free) + \$60 + 120 + \$50 = \$230 + 1 Velcro compression garment
 - d. Subgroup Aim 3 each one-time visit treatment (pre and post MRI and non MRI measures = \$80

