1. We will utilize multi-parametric anatomical and molecular imaging of LNs, which incorporate measures of anatomy and chemical environment, to evaluate abilities to discriminate metastatic from benign LNs noninvasively *in vivo*. These approaches have already been applied in other applications of malignancy⁵⁻⁷, and we have developed innovative high spatial resolution variants to enable sub-millimeter LN characterization *in vivo*¹. If successful, findings would have relevance for noninvasively mapping the topography of LN malignancy, which could initiate future investigations to ultimately inform surgery decisions and reduce unnecessary LN removal.

2. We will extend our current trial to evaluate sub-clinical internal and external risk factors of secondary lymphedema progression in the arm and upper torso following cancer therapies post-LN removal and test more refined hypotheses regarding how impaired lymphatic pumping, superficial axillary water accumulation, and interstitial adipose accumulation portend secondary lymphedema onset and progression. This work will be significant for understanding prognostic potential of the new internal markers relative to existing risk factors, and it will reinforce using these measures to triage patients for disease-modifying therapies or as endpoints in therapeutic trials.

3. Emerging therapies that utilize CDT with refined approaches in the individual components (i.e. incorporating graded negative pressure) are being utilized in specialized lymphedema outpatient clinics including Vanderbilt Lymphedema Clinic, but formal efficacy trials have not been performed. We will perform a multiple-measures cross-over trial to evaluate the impact of CDT with vs. without graded negative pressure on reducing lymph stasis and internal markers of fibrosis in chronic BCRL states, along with a subgroup of 1 time treatment before and after MRI and nonMRI measures for immediate treatment impact investigation. Improved lymphatic flow has demonstrated the ability to induce lymphangiogenesis in pre-clinical studies⁸, and it will be crucial to demonstrate internal improvements in vivo, relative to basic symptomatology changes which can be subjective and difficult to quantify, to underscore the need for expanding healthcare coverage of these disease-modifying therapies.

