Aim 1: Prevention. We will apply new anatomical and functional LN imaging approaches to identify LN profiles specific to biopsy-confirmed metastatic LNs; findings could be used to better inform LN removal and reduce the incidence of benign LN dissection. We will incorporate healthy female controls to serve as a comparison to the patient population.

Aim 2: Progression. We will improve our understanding of secondary lymphedema risk progression following cancer therapy by testing the hypothesis that superficial tissue profiles and subcutaneous adipose accumulation are more prevalent in patients experiencing lymphedema progression, and thereby could be used to triage patients for aggressive therapies prior to overt symptoms and irreversible damage.

Aim 3: Therapy. We will perform a repeated-measures cross-over trial to test the hypothesis that mobilization of protein enriched hardened tissue using graded negative pressure therapy in conjunction with complete decongestive therapy (CDT) is more effective to standard CDT alone for secondary lymphedema management. Both of these conservative physical therapy treatments are commonly employed for treatment of secondary lymphedema and the Vanderbilt Lymphedema Clinic utilizes the graded negative pressure therapy as a component of treatment. Additionally we will perform a subgroup of 1-time only hour treatment with before and after MRI and nonMRI measurements for additional immediate treatment impact in CDT, CDT with graded negative pressure, or exercise and self management treatment strategies alone as commonly performed in outpatient physical therapy clinics and at home for the management of BCRL.

The overarching goal is to develop objective markers of lymphatic dysfunction that can be used in emerging therapeutic trials of cancer and lymphedema therapies to be used to reduce both the incidence and severity of symptoms associated with this prevalent and chronic condition.

Aim (1). To compare *in vivo* anatomical and novel molecular imaging contrasts between LNs with versus without biopsy-confirmed metastasis.

Hypothesis (1). Biochemical LN profiles quantified from noninvasive chemical exchange saturation transfer (CEST) MRI provide discriminatory potential for distinguishing metastatic versus benign LNs pre-operatively. These biochemical profiles are more discriminatory than anatomical measures of LN morphology.

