8.0 Statistical analysis plan

Statistical analysis will be overseen by statistician co-investigators. Means, standard deviations, and ranges for continuous variables will be recorded, along with tests for normality and homoscedasticity. The primary statistical objective is to assess whether the changes, pre- vs. post-intervention, in internal imaging metrics of lymphatic clearance or PSFS score are different for the standard CDT therapy or CDT therapy with negative pressure. First, a Student's t-test or Wilcoxon signed-rank test (depending on normality results) will be applied to test the difference between each measurement for the same subject for each of the two therapy sessions. We will also test the difference of any potential carryover effect and we will apply a general linear model approach, in which we include the treatment and treatment-period interaction in the model. Power calculations are based on our preliminary data that observed an improvement in PSFS in five patients on CDT with negative pressure vs. CDT alone, as well as an ability to detect a mean change in T_2 and lymphangiography score pre- vs. post-MLD of N. With the premise that CDT with negative pressure will be at least as good as CDT without negative pressure, with the proposed sample size, we will have 80% power to detect a 40% reduction rate with one-sided type I error = 5%.

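### Section 5.0 item 5 gives both Aim 3 groups the same treatment order, so the planned cross-over comparison cannot separate treatment from course

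*Combined protocol and SAP*

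**What the plan says.** **Declared design.** Section 1.0 (significance item 3) states: "We will perform a multiple-measures cross-over trial to evaluate the impact of CDT with vs. without graded negative pressure". Section 2.0, Aim 3, says the same: "We will perform a repeated-measures cross-over trial to test the hypothesis".

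**Treatment order.** Section 5.0 item 5 introduces the two courses with: "Then they will receive their assigned therapy intervention (CDT alone or CDT with graded negative pressure) at Visits 2-10 and 13-21". For the first group it then says: "For Group 1, the first course of treatment will be CDT alone, then the second course of treatment will be CDT with graded negative pressure". The sentence on the second group reads: "For Group 2, the first course of treatment will be CDT alone, then the second course of treatment will be CDT with graded negative pressure". Apart from the group number, the two sentences are identical.

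**Measurement.** Item 5 says of the Aim 3 subjects: "they will receive the above mentioned non-MRI and MRI measures (#2) at Visits 1, 11, 12 and 22". Each course therefore has its own pre-measure (Visits 1 and 12) and post-measure (Visits 11 and 22).

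**Analysis.** The primary objective in section 8.0 asks whether the pre-to-post changes "are different for the standard CDT therapy or CDT therapy with negative pressure". A paired test within subject comes first. A carryover test and a general linear model with treatment and treatment-by-period terms follow.

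**Nothing elsewhere changes the order.** The section headed "4.0 Enrollment / Randomization" describes recruitment only. Section 10.0 covers the scheduling of both courses and gives no order.

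**The concern.** A two-treatment, two-period cross-over separates treatment from period because some subjects receive the treatments in one order and the rest in the other. With one order for everyone, CDT alone is always course 1 and CDT with negative pressure is always course 2. Anything that makes the amount of change differ between courses is then credited to, or subtracted from, negative pressure. Examples are a time trend, residual benefit from course 1, regression to the mean, and familiarity with a self-reported score such as the PSFS, which the primary objective names.

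At stake is the primary comparison of the two-course part of Aim 3. It could show a benefit that does not exist or hide one that does, and no later analysis of a single-order data set could tell which. The one-time treatment subgroup (section 5.0 item 6) is not affected.

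**Working it through.** **1. The plan's own figure.** Section 8.0 claims 80% power for a 40% reduction rate at one-sided 5%. It cannot be reproduced, because the documents give no sample size, SD or baseline rate. The point does not depend on it.

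**2. Can the model be estimated?** Write A for CDT alone and B for CDT with negative pressure. Take two groups, two courses and two subjects per group. The order comes from item 5 and the first model below from section 8.0. Section 8.0 does not mention subject effects, so the other two models are added here as the usual cross-over forms.

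| Columns | A-B in both groups (as written) | A-B and B-A |
|---|---|---|
| Correlation of treatment with course | 1.0 | 0 |
| Rank of intercept, treatment, treatment × period | 2 of 3 | 3 of 3 |
| Rank of subject, period, treatment | 5 of 6 | 6 of 6 |
| Rank of subject, period, treatment, treatment × period | 5 of 7 | 6 of 7 |

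As written, the treatment-by-period term is redundant: it equals the treatment column under 0/1 coding and the intercept under ±1 coding. With differing orders and ±1 coding, it is +1 throughout one group and −1 throughout the other, so it is the sequence contrast. That is why the last model stays one rank short once subject effects are fitted.

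**3. What does the paired test estimate?** For each subject let D = (Visit 22 − Visit 12) − (Visit 11 − Visit 1). With a single order,

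E(D) = (treatment effect of B over A) + (course 2 minus course 1 difference in the amount of change).

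A constant level shift at Visits 12 and 22 cancels; a difference in the amount of change does not. A simulation with no treatment effect (40,000 runs, n = 20) confirms this. A level shift of 1 SD gives mean D = 0.00 and 4.9% rejections. A 0.5 SD difference in change gives mean D = 0.50 and 69.7% rejections.

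**4. Illustration of size.** Everything here is assumed: no treatment effect, SD of D equal to 1, and a between-course difference d. The rejection rate of the one-sided 5% paired t-test is P(T > t₀.₉₅,ₙ₋₁), where T is non-central t with n − 1 degrees of freedom and non-centrality d√n. For n = 20 the critical value is 1.729. With d = 0.2 the non-centrality is 0.2 × √20 = 0.894 and the rate is 21.7%. With d = 0.5 it is 0.5 × √20 = 2.236 and the rate is 69.5%.

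| n | d = 0.2, favours course 2 | d = 0.5, favours course 2 | d = 0.2, favours course 1 | d = 0.5, favours course 1 |
|---|---|---|---|---|
| 10 | 14.5% | 42.7% | 1.28% | 0.09% |
| 20 | 21.7% | 69.5% | 0.61% | 0.01% |
| 40 | 34.4% | 92.8% | 0.19% | <0.01% |

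**5. After the orders differ.** With equal groups, period in the model and equal carryover, simulated rejection under no treatment effect is 4.9% to 5.3% for n = 20 or 40 and d from 0 to 0.5. The unadjusted paired test is then conservative: 3.4% at n = 20, d = 0.5.

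Unequal carryover is not removed, because half of it enters the treatment estimate. If carryover of 0.25 to 0.5 SD lowers the change in the course after negative pressure, the period-adjusted test rejects 13% to 29% of the time at n = 20 (10% to 18% at n = 10, 19% to 46% at n = 40). In the other direction it rejects at most 1.5% at n = 20.

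**The case against.** The strongest reply is that this is a drafting slip. Two labelled groups, an assigned therapy, analysts blinded to group assignment (section 5.0 item 7) and a treatment-by-period analysis all presuppose two orders. That reading is probably right. But item 5 is the instruction that governs delivery, it is complete and grammatical, and no other text overrides it. Harm follows only if it was or will be followed, and the documents do not settle that.

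Three narrower objections have force:

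- The paired test, or a model with treatment alone, still runs under a single order. What fails is estimating the treatment-by-period term and separating treatment from course.
- Comparing Visit 12 with Visit 1 gives a rough check for a residual level shift, mixed with any time trend. What has no comparison group is carryover assessed through the treatment-by-period term, which is the only form section 8.0 indicates.
- The rejection rates reflect assumed sample sizes and effects, and say nothing specific about this trial. The confounding itself needs no such assumption.

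None of these removes the contradiction or its effect on the primary comparison.

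**Conclusion.** The concern holds. Item 5 contradicts the declared cross-over and the section 8.0 analysis. Followed as written, it makes treatment and course the same variable in the two-course part of Aim 3. The structural result (correlation 1.0, the section 8.0 model at rank 2 of 3) follows from the order in item 5 and the terms named in section 8.0. The size and direction of any bias are unknown. The rates of 22% to 70% or 0.6% and below at n = 20 only show how sensitive the planned test would be under the stated assumptions. That item 5 is a copying error is an inference. Whether any treated subject is affected cannot be told from the documents.

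**What to change.** - **Section 5.0 item 5:** reconcile with sections 1.0, 2.0 and 8.0 so that the two groups' sequences differ, as a cross-over requires. Which group takes which sequence is for the sponsor to state.
- **Section 4.0:** add how subjects are allocated to sequence.
- **Records:** confirm and document the order each subject actually received. If all subjects treated so far had one order, report for them that treatment and course cannot be separated.
- **Section 8.0:** estimate treatment within subject with period in the model. Test carryover as a between-subject comparison of sequences, since the treatment-by-period term is aliased with sequence once subject effects are fitted. State that differing sequences remove period bias but not bias from unequal carryover.

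Because carryover matters here, the washout length also needs reconciling: item 5 gives it as 4–8 weeks and item 9 as 4–8 months.

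The cost is a short amendment to three sections and a check of treatment records. If subjects have already been treated in a single order, the amendment protects later subjects but does not recover the comparison for those already treated.

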10.0 Follow-up

No specific follow-up scans are required for Aim 1 unless patients are eligible and would like to enroll in the 2-year monitoring aim of the study (Aim2). For Aim 2, subjects will be able to contact the PI and co-investigators with any questions and a KSP will contact them to schedule their 6-8 month follow up visits for a total of 4 within the 2 year monitoring period. For Aim 3, subjects will be scheduled for all treatment visits prior to start of each course of treatment (Visits 2-10 and 13-21). The subjects will be able to contact the KSP with any questions and needs to change their assigned treatment times and dates should any adjustments be necessary. The subjects will be contacted during their washout period to schedule their second course of treatment visits and intake and exit measurement visits. An unwillingness to participate in any future scans or treatments will not influence or disqualify a volunteer from participating in the first instance. For the one-time treatment subgroup of Aim 3, this is a one-time visit for the pre and post MRI and nonMRI measures with no further study follow-up unless the participant wishes to undergo all three separate treatment interventions at different dates for interperson treatment comparison. For participants in Aim 2 (monitoring period), if the lymphedema specialist recommends lymphedema management, then the subject will be encouraged to seek out clinical care which does not prevent them from being able to participate in this study, including patients being monitored over 2-years. The lymphedema specialist will help the client obtain orders and location of treatment if subject would like assistance.

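### Section 5.0 contradicts itself on two Aim 3 cross-over features: the washout is in weeks in one place and months in another, and both groups get the same treatment order

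*Combined protocol and SAP*

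**What the plan says.** **Washout.** Section 5.0 item 5 sets out the Aim 3 visits. Measurements are at Visits 1, 11, 12 and 22, and treatment is at Visits 2-10 and 13-21. It then says "There will be a 4-8 week washout period between Visit 11 and Visit 12". Item 9.c of the same section lists the Aim 3 payments in time order. Between the payment for finishing the first nine treatments with exit measures and the payment for the first scan of the second treatment, it has the line "After 4-8 month washout period". Section 10.0 mentions the washout without a length: "The subjects will be contacted during their washout period to schedule their second course of treatment visits".

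**Order.** Section 5.0 item 5 says "For Group 1, the first course of treatment will be CDT alone", followed by CDT with graded negative pressure as the second course. The next sentence says "For Group 2, the first course of treatment will be CDT alone", again followed by CDT with graded negative pressure. Sections 1.0 and 2.0 call Aim 3 a cross-over trial.

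**Analysis.** The primary statistical objective in Section 8.0 is to assess "whether the changes, pre- vs. post-intervention, in internal imaging metrics of lymphatic clearance or PSFS score are different" between the two therapies. The section adds "We will also test the difference of any potential carryover effect" and, for the general linear model, "we include the treatment and treatment-period interaction in the model".

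**The concern.** Washout length and treatment order are basic design features of a two-period cross-over, and the analysis in Section 8.0 relies on both.

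The washout contradiction is first an operational problem. Whoever schedules Visit 12 cannot satisfy both statements. Section 6.0 requires protocol deviations to be reported to the IRB within ten working days, yet for many Visit 12 dates the protocol does not say whether there is a deviation. It is also a statistical matter, because the interval affects how much of the first course's effect is still present when the second course is measured.

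The order text has the heavier consequence. If both groups receive the two therapies in the same order, the comparison of therapies is also a comparison of first course with second course, and no choice of washout repairs that.

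**Working it through.** **1. Do both lines describe the same interval?** Item 5 names it as Visit 11 to Visit 12. Item 9.c.iii places it after the exit measures of course 1 (Visit 11) and before the first scan of course 2 (Visit 12). They are the same interval.

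**2. Do the ranges overlap?**

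| Statement | Days | Weeks |
|---|---|---|
| Item 5, 4-8 weeks | 4 × 7 = 28 to 8 × 7 = 56 | 4 to 8 |
| Item 9.c.iii, calendar months (365.25/12 days) | 121.75 to 243.5 | 17.4 to 34.8 |
| Item 9.c.iii, 28-day months (most lenient) | 4 × 28 = 112 to 8 × 28 = 224 | 16 to 32 |

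The longest washout under item 5 is 56 days. The shortest under item 9.c.iii is 121.75 days, a gap of 65.75 days or 9.4 weeks. With 28-day months the gap is 112 − 56 = 56 days, or 8.0 weeks. A 5-week interval meets only item 5, a 20-week interval meets only item 9.c.iii, and a 12-week interval meets neither.

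**3. Effect on time in the study.** Each course takes 6-8 weeks, so two courses take 12-16 weeks. Adding the washout gives 12 + 4 = 16 to 16 + 8 = 24 weeks under item 5. Under item 9.c.iii it gives 12 + 17.4 = 29.4 to 16 + 34.8 = 50.8 weeks (28 to 48 with 28-day months). Time for measurement visits is not added.

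**4. The order text as written.** Let tA and tB be the mean within-course change on CDT alone (A) and on CDT with negative pressure (B). Let p1 and p2 be the period effects. Let rA and rB be the part of the course 1 effect lost between Visits 12 and 22. If everyone has A then B, course 2 minus course 1 estimates

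(tB − tA) + (p2 − p1) − rA.

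There are two course means for four unknowns (overall mean, period, treatment, carry-over), so the design has rank 2 of 4. In the terms of Section 8.0, code treatment A = 0, B = 1 and period 1 = 0, period 2 = 1. The treatment column then equals the period column, and their product (0 × 0 = 0, 1 × 1 = 1) equals both. The interaction term cannot be estimated, and the washout length does not enter this argument.

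**5. If the orders were opposite.**

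- A then B: (tB − tA) + (p2 − p1) − rA
- B then A: (tA − tB) + (p2 − p1) − rB
- Half the difference: (tB − tA) + (rB − rA)/2

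Mean, period, treatment and one differential carry-over term are then estimable (rank 4 of 4), provided there is no separate sequence effect. Under this additive model the bias is (rB − rA)/2.

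The model assumes that the change during a course does not depend on its starting level. Suppose instead that course 2 change falls by b for each unit of course 1 effect still present at Visit 12, with sA and sB present after A and B. The two lines then gain −b·sA and −b·sB, and half the difference gains b(sB − sA)/2. A residual that is stable, but unequal between therapies, then also matters. Under either model, the quantities concerned depend on how much of the course 1 effect survives the washout.

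**The case against.** The strongest case on the other side is that the two washout statements do not have equal standing. Item 5 is the visit schedule. Item 9.c.iii is a line in a payment list that sets no payment and repeats the same digits, so a slip in the unit is plausible. Nothing shows that scheduling would follow the payment list. This limits the practical risk, but it does not settle the text: both lines are current, and no section says which unit is meant.

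A similar case can be made for the order text. The second sentence may be a copying error, since two groups with the same order would serve no purpose, and Section 5.0 item 7 blinds the analysts to group assignment. That makes an intended difference plausible, but the documents never state a second order. It can also be said that a design in which everyone receives both therapies in one order is loosely a cross-over. Such a design would still not support the carry-over test in Section 8.0.

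It is fair to add that the order problem is separate from the washout and more serious, and that no consequence of the washout discrepancy has been quantified. Both remarks stand.

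A reader might infer more than the documents support:

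- *That bias can arise only if residual effects fade at different rates after the two therapies.* This needs an additive model in which change is unrelated to the Visit 12 level, and the documents give no basis for that assumption.
- *That the trial is in fact run in a single order.* The text says so literally, but it conflicts with the stated design.
- *That one of the washout lengths is inadequate.* The documents give no duration of effect against which to judge either.

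**Conclusion.** The point holds as two contradictions in the text of Section 5.0, and both should be corrected.

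- **Washout:** two non-overlapping ranges for one interval, at least 8.0 weeks apart on the most lenient reading of a month. This rests only on both lines meaning Visit 11 to Visit 12, which their positions show.
- **Order:** identical sequences for Groups 1 and 2, against a trial described as a cross-over. If followed literally, treatment, period and carry-over cannot be separated and the carry-over analysis in Section 8.0 cannot be carried out, whatever the washout.

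If the orders are opposite, washout length bears on possible carry-over. No size or direction of bias is claimed. The documents give no duration of effect, and they state no Aim 3 sample size or group sizes from which an effect on power could be worked out.

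**What to change.** 1. Reconcile Section 5.0 items 5 and 9.c.iii so that one washout appears in both places. The sponsor decides which stands.
2. Reconcile the Group 1 and Group 2 order text in Section 5.0 item 5 with the cross-over named in Section 2.0, and check that the carry-over test and interaction model in Section 8.0 can be fitted to the order that results.
3. Optionally, derive each participant's actual interval from Visit 11 to Visit 12, so that it is available to the Aim 3 analysis.

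The first two are wording changes within Section 5.0. The third needs one variable computed from two visit dates. No extra visits or measurements are required.
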